4.1 Inclusion Criteria

1. Participant must have at least five minutes of chest pain or equivalent (chest tightness; pain radiating to left, right, or both arms or shoulders, back, neck, epigastrium, jaw/throat; or unexplained shortness of breath, syncope/presyncope, generalized weakness, nausea, or vomiting thought to be of cardiac origin) at rest or during exercise within 24 hours of ED presentation, warranting further risk stratification, as determined by an ED attending.
2. Participant must be able to provide a written informed consent.
3. Participants must be <75 years of age, but ≥ 40 years of age.
4. Participant must be able to hold breath for at least 10 seconds.
5. Participant must be in sinus rhythm.

4.2 Exclusion Criteria

1. New diagnostic ischemic ECG changes (ST-segment elevation or depression > 1 mm or T-wave inversion > 4 mm) in more than two anatomically adjacent leads or left bundle branch block
2. Documented or self-reported history of CAD (MI, percutaneous coronary interventions [PCIs], coronary artery bypass graft [CABG], known significant coronary stenosis [$>50\%$])
3. Greater than 6 hours since presentation to ED to time of consent.
4. BMI >40 kg/m²
5. Impaired renal function as defined by local standard of care - for example, measured serum creatinine >1.5 mg/dL
6. Markedly elevated troponin as defined by local standard of care
7. Hemodynamically or clinically unstable condition (BP systolic < 80 mm Hg, atrial or ventricular arrhythmias, persistent chest pain despite adequate therapy)
8. Known allergy to iodinated contrast agent
9. Currently symptomatic asthma
10. Documented or self-reported cocaine use within the past 48 hours (acute)
11. On Metformin therapy and unable or unwilling to discontinue for 48 hours after the CT scan

12. Contraindication to beta blockers (taking daily antiasthmatic medication): This exclusion only applies to patients with a heart rate > 65 bpm at sites using a non-dual source CT scanner
13. Participant with no telephone or cell phone numbers (preventing follow-up)
14. Participant with positive pregnancy test. Women of childbearing potential, defined as <2 years of menopause in the absence of hysterectomy or tube ligation, must have a pregnancy test performed within 24 hours before the CT scan.
15. Participant unwilling to provide a written informed consent.

4.3 Recruitment, Screening, and Consent

The research team at each participating site includes the ED attending physician, CT technologist, and research associate(s). The investigator and the research staff will be responsible for the screening, review of participant medical records and investigator-designated data submission. All clinical sites will perform screening Monday through Friday during daytime hours (9am-5pm). Potential subjects will be identified by research coordinator/study nurse staff shortly after admission to the ED usually after the initial ED evaluation consisting of ECG, physical examination, clinical symptoms and presentation, immediate and past medical history has been concluded and screened for eligibility based on a checklist providing inclusion and exclusion criteria.

Eligible subjects will be approached and, if the subject considers participation, the Clinical Research Coordinator (CRC) will describe the rationale of the study, the study procedures with associated risks and benefits. A study physician/study nurse/CRC will speak directly with an ED physician caring for the patient to obtain an assessment of pretest probability for ACS and will verify that the ED physician feels that further observation or diagnostic testing is warranted in this patient.

If the subject agrees and further testing or observation is planned as SOC, key study personnel, typically a study physician or the attending ED physician, will review the study procedures, as well as all potential risks and discomforts and the opportunity to decline or cease participation in the study at any time, answer any remaining questions, and consent the subject.

Patients can be consented but not randomized before the first troponin test result is available. Patients whose initial troponin level is markedly elevated will not be randomized and will not be included in the intent-to-treat population. Patients whose subsequent troponin testing is markedly elevated will be included in the intent to treat population.

Patients can be consented before a pregnancy test is available. However, patients with a positive pregnancy test will not be randomized.

Patients who are not randomized will not be considered part of the intent to treat population.

Informed Consent:

- A potential subject will then be afforded as much time as clinically feasible to review the consent form and decide upon their participation without adversely effecting their ED care, which is typically 1 hour.
- If the ED staff caring for the patient determines that the potential subject's previously determined plan of care must proceed before the potential subject has had adequate time to decide upon his/her participation without undue pressure, the potential subject will be excluded from enrollment.
- Subjects will be provided with a copy of the informed consent form.

4.4 Randomization

After the patient has been consented by the study physician, the study subject will be randomized into the standard care arm or the intervention arm (cardiac CT) by means randomization stratified by institution using a central computerized randomization system.

5. Study Procedures

5.1 Index Hospitalization

Standard of Care Arm: Subjects will be evaluated according to each hospital's specific protocol to evaluate and manage patients with acute chest pain. Typically, the standard evaluation in the ED will include the past and current medical history, a physical examination, an ECG and a cardiac biomarker (Troponin and CK-MB) as well as other routinely obtained blood testing. Patients may undergo cardiac CT as part of SOC but only as a secondary diagnostic test. Patients in the CT arm may undergo further diagnostic testing as well.

All admitted subjects will undergo each hospital's standard rule out myocardial ischemia protocol. This protocol typically consists of observation and monitoring including serial ECGs and repeated cardiac biomarker measurements as well as a noninvasive stress test (often imaging based) to evaluate for myocardial ischemia. The participating clinical sites perform routinely either nuclear perfusion imaging [SPECT] at rest and stress, and/or stress echocardiography, and/or exercise treadmill test [ETT]. Depending on the results, subjects may undergo additional noninvasive or invasive testing (coronary angiography), and/or coronary revascularization during their hospital stay.

Interventional Arm: In subjects randomized to the intervention arm, a contrast enhanced cardiac CT will be performed (after initial troponin level is available) in addition to the initial ED evaluation.

The ED physicians will resume care of the patient and make all clinical decisions for further care of the patient (e.g., need for further evaluation or admission) based upon their cumulative clinical assessment of the patient, including findings revealed on the CT scan.

In addition, in patients from both study arms who consented to a blood draw, we will obtain three fifteen (15) mL venous blood samples over a six-hour period, less than forty-five (45) mL in total. Blood samples will be centrifuged and frozen for future analysis for cardiac-related markers.

All diagnostic tests will be performed per Society Guidelines. Cardiac Computed Tomography is performed in accordance with best practice standards as delineated in the imaging guidelines of the Society of Cardiovascular Computed Tomography by competent⁶³ and appropriately credentialed physicians. This includes the optimization of the scan protocol to limit radiation exposure.

5.2 48-72 Hour Follow up after ED discharge

Follow-up phone call at 48-72 hours: Subjects who are discharged from the ED within 24 hours of presentation (for both randomization arms) will be contacted via telephone between 48 and 72 hours after discharge to avoid ascertainment bias. During this call, subjects will be interviewed to determine whether they have had any recurrent symptoms suggestive of myocardial ischemia and and/or whether they needed to seek further medical attention following their emergency department visit. If these phone attempts at 48 and 72 hours are not successful, a final attempt will be made at 96 hours to contact the subject

NOTE: If a subject is discharged on a Thursday, the 48-72 hour phone call may be extended to 96 hours. In the rare circumstance that a subject is discharged on a Thursday and the following Monday is a holiday, the follow-up call can be made during the next working business day.

5.3 28 Day Follow up

Follow up 28 day phone call: All subjects will be interviewed via a telephone call 28 days post ED discharge (+4 weeks) to determine the occurrence of MACE and healthcare utilization using a standardized questionnaire. All cases of recurrent chest pain, hospital admissions, and diagnostic testing will be verified by review of medical records.

A reminder letter will be sent or phone call will be made to participants, two weeks prior to the 28-day follow up phone call. If unable to contact the participant by phone, mortality will be assessed online using the SSDI website.

6. Data Collection

The following subject data will be collected during index ED visit/hospitalization and follow up phone interviews:

- Subject demographic information
- Medical history, including cardiac risk factors and medications
- Description of recent pain episodes
- Vitals signs, ECG, cardiac biomarker results
- Cardiac CT imaging and other cardiac-related diagnostic testing data
- Adverse events

7. Statistical Considerations

A total of 1000 participants will be enrolled in this study. Enrollment is planned to be completed in 15 months.

	Group A (Standard Eval.) N=500	Group B (CT Eval.) N=500		
65%	40.5 (\pm 43.2)	32.8 (\pm 46.7)	-8.3	83%
70%	40.5 (\pm 43.2)	30.5 (\pm 45.5)	-10.1	95%
80%	40.5 (\pm 43.2)	26.3 (\pm 41.7)	-14.2	99%
90%	40.5 (\pm 43.2)	22.4 (\pm 37.3)	-18.1	>99%
100%	40.5 (\pm 43.2)	18.8 (\pm 33.5)	-21.7	>99%

7.2 Secondary Aims

To compare the two study arms in terms of time to diagnosis and rates of direct discharge.

The time to discharge (defined as time from ED presentation until discharge to home) will be plotted using Kaplan-Meier curves because some patients will be in the hospital at 30 days post day of presentation/randomization. The curves for the two groups will be compared using a test based on the difference in the average length of stay in the two groups (truncated at 30 days) divided by the standard error of this difference.⁶⁰ We choose this test because the average length of stay is most closely associated with cost. It will be also instructive to compare the curves themselves as they will provide information on the effect of cardiac CT on different groups of patients. For instance one group of patients, those who are discharged due to cardiac CT, may have a shorter length of stay, while others may have a longer length of stay due to waiting for the results of the CT or other procedures that the CT indicates.

Sample Size: The planned sample size will also provide adequate power to detect the rates of direct discharge from ED. Screening data from a site survey of our clinical sites as well as published data indicate that the standard ED discharge rate is approximately 15% in the target population.

According to our preliminary data and data from other groups, we expect that 40% to 50% of participants have no detectable CAD by cardiac CT. The negative predictive value of this finding for ACS has been shown to be 100%. Our guidelines suggest that these participants will be discharged directly from the ED. However, realistically, we expect that because of administrative issues and remaining individual variation of the decision to discharge depending on the clinical presentation of participants actually only 60% to 80% of these participants will be discharged. Thus, anywhere from 24% to 40% participants could be discharged directly from the ED in the interventional arm. For the sample size analysis, we assume that 32% of participants will be discharged.

Based on the aforementioned key assumptions, for the *Standard Evaluation* we anticipate that 15% of all participants will be discharged and 85% will be admitted (discharge rate: 15%). For the *Cardiac CT Evaluation*, we assume a discharge rate of 32%. For the objective of superiority

of discharge rates we will have a 100% chance at a significance level of 0.05 to detect a 17% increase in discharge rates from 15% to 32%.

The comparison of time to discharge among patients who are admitted to the hospital is complicated by the fact that the two groups will not be the same group of patients. For instance, patients who would have been discharged in the cardiac CT group but admitted in the usual care group may have a relatively shorter time post admission than patients who would have been admitted in both groups. We have developed methods for analyzing these types of data using causal inference that will be applied to this analysis.⁶¹ A similar analysis will be applied to other subgroups such as those with and without ACS.

To compare the two study arms in terms of cardiac health care utilization during the index visit. Health care utilization components will include invasive coronary angiograms and coronary revascularization..

The analysis for this secondary aim will be performed from the intent to treat perspective. Health care utilization will be assessed using medical record review. Measures of key components of utilization will be compared across the two study groups using procedures appropriate for each measure (rate or count).

In particular the two arms will be compared in terms of the number of invasive coronary angiograms. This secondary endpoint will be analyzed in terms of a non-inferiority trial. In a non-inferiority trial the null hypothesis is that cardiac CT is worse than usual care in that the rate of coronary angiograms is increased and the alternative hypothesis is that it is not in worse and the rate of angiograms is the same. The reason for reversing the usual null and alternative hypothesis is that the purpose of this analysis is to prove that cardiac CT is not worse than usual care, this would not be accomplished by just showing that the difference between the two was not significant.

Screening data from a survey of clinical sites as well as published data indicate that the standard rate of invasive coronary angiograms in the target population is approximately 10%. According to our study guidelines we assume that most but not all participants with significant stenosis in CT (10% of participants) undergo invasive coronary angiography (notably those who also have a positive stress test and those who have high grade proximal stenosis or LAD stenosis). In addition, we assume that a minority of participants with indeterminate stenosis (<5%) and positive stress testing undergo invasive coronary angiography. Because of the moderate specificities of standard diagnostic testing up to 40% of participants who undergo cardiac catheterization have no significant CAD.^{15,16} Because the diagnostic accuracy of cardiac CT for the detection of coronary stenosis is comparable or better than standard diagnostic testing, we believe that there will be no increase in the rates of invasive coronary angiograms. If we define a 5% difference as an “acceptable” difference in cardiac catheterization rates than we will have an 84% chance of showing that the CT arm is significantly less than 5% worse than the standard arm at a one sided $p=0.05$ significance level.

Another key measure of utilization is the number of coronary revascularization procedures: In ROMICAT I there were 18 revascularization procedures performed in 368 patients (5%). Thus, we expect 5% procedures in the standard evaluation. If we assume that not all participants with significant stenosis will undergo coronary revascularization (because if no MI it can be medically managed) and that cardiac CT may also avoid some angiograms by excluding disease, than we can realistically assume that there is not a difference between the two study arms. If we consider this in terms of a non-inferiority trial as above, we will have 80% power to rule a difference of 3.5%.

To compare the two study arms in terms of cardiac health care utilization within one year after index hospitalization. Health care utilization components will include invasive coronary angiograms, cardiac related diagnostic and lab testing, and ED visits.

This analysis will be performed from the intent to treat perspective. CP and CT related health care utilization will be assessed using medical record review. Measures of key components of utilization will be compared across the two study groups using procedures appropriate for each measure (rate or count).

We expect that the rate of additional cardiac work-up will be 29% in the SOC arm and will be 14% in the interventional arm. We will have >95% power to detect this difference.

We expect that the rate of hospital admissions with additional diagnostic cardiac testing will be 9.3% in the SOC arm and will be 4% in the interventional arm. We will have >95% power to detect this difference.

We expect that the rates of these measures will be associated with the CT findings at index hospitalization.

To evaluate the cost and cost-effectiveness of incorporating cardiac CT into the standard ED evaluation of patients with acute chest pain

These analyses will be performed by the Decision Analysis and Cost-Effectiveness Center (DACE). Therefore, the sites will collect and provide the necessary data to the DACE and the costs will be derived from the cost-accounting database (TSI). As a first step, incorporating cardiac CT into the standard evaluation of patients with acute chest pain will be tested for cost-saving over a 28-day and lifetime span as compared to standard care. Further on, cost-effectiveness of incorporating cardiac CT into the standard ED evaluation of patients with acute chest pain will be determined using first-order Monte Carlo microsimulations.

To compare the two study arms in terms of rates of MACE (cardiac death, AMI, revascularization, unstable angina, and rehospitalization) within 28 days.

The analysis for this secondary aim will be performed from the intent to treat perspective. The occurrence of MACE will be assessed via patient follow-up and medical chart review. The primary analysis for this aim will be performed at the patient level by determining whether any MACE occurred or not. Event rates will be estimated and compared between study groups using exact procedures. In a secondary analysis, the rates of each type of MACE will be examined separately.

Sample Size- Safety Considerations- Missed ACS: Mistaken discharges are the primary safety issue in this study. All available data indicate that the absence of any detectable CAD (absence

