Secondary Endpoints	
 • The time to diagnosis: For ACS, defined as the time from ED presentation until the first test during index hospitalization that leads to the diagnosis of ACS (tests may be biomarkers, CTA, ETT, nuclear imaging, stress ECHO or cardiac catheterization); for no ACS, defined as the time from ED presentation to the final test during index hospitalization. • Admission to hospital: Participants are considered to be admitted if the ED attending admitted the subject to a hospital floor (medical floor, step down unit, telemetry hospital floor or intensive care unit). • Direct ED discharge: will include all subjects who are not admitted to the hospital. • Health care utilization: number of invasive coronary angiograms, diagnostic (imaging) tests, interventions, repeat ED visits. • Rates of MACE: major adverse cardiac events – cardiac death, acute myocardial infarction, revascularization, unstable angina and rehospitalization. • Cost of care derived from the cost-accounting database (i.e., TSI).
Tertiary Endpoints	Increased test burden: Further imaging tests performed after index hospitalization
Primary Hypothesis	Adding cardiac CT to the initial ED evaluation of subjects with acute chest pain significantly decreases length of hospital stay.

Secondary Hypothesis	Addition of cardiac CT to the initial ED evaluation of subjects with acute chest pain will significantly increase the ED discharge rate, and shorten the time to diagnosis and it will be a cost-saving and cost-effective modality. There will not be an increase in the number of invasive angiograms or coronary revascularization procedures as compared to the SOC arm. With a high negative predictive value, patient safety will not be compromised. There will not be an increase in subsequent further testing and the rate of MACE in both arms in the follow-up period will be similar. The test characteristics of contrast enhanced CT will be significantly better than that of a non-contrast CT.
Study Design	The study is designed as a randomized diagnostic multicenter trial and will enroll 1,000 participants at seven sites over a 15 month period. Participants presenting with acute chest pain in the ED will be randomized to standard of care (SOC) or to an interventional arm. Patients in the interventional arm will receive standard evaluation supplemented by contrast-enhanced cardiac CT imaging

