In both arms, the initial Emergency Department (ED) evaluation (electrocardiogram [ECG], physical examination, clinical presentation, renal function lab, and medical history) will determine eligibility of patients. After randomization, standard of care will be performed in both arms. However, for patients randomized to the interventional arm, a CT will be performed. The following decisions made by the caregiver team will be tracked: admission or discharge after initial ED evaluation plus CT/other initial diagnostic test, in admitted participants, the length of hospital stay, the extent of further testing including serial cardiac markers and ECG, and other diagnostic tests or interventions. For safety reasons, participants discharged in less than 24 hours of ED arrival will receive a phone call 48-72 hours after discharge. All participants will receive a 28-day follow-up phone interview. The efficiency of each strategy will be determined by comparing 1) the length of hospital stay (primary endpoint), 2) the time to diagnosis (secondary endpoint), 3) the rates of ED discharge (secondary endpoint), 4) utilization of other diagnostic testing, i.e. invasive coronary angiograms, and resulting interventions, i.e. coronary revascularization procedures during index hospitalization and 28 days (secondary endpoint). The safety of the two strategies will be compared by determining the occurrence of adverse events within 48-72 hours in directly discharged patients as well as determination of major adverse cardiovascular events (MACE) within 28 days after discharge from the index hospitalization. We will also perform a cost and cost effectiveness analysis. In subsequent analyses, we will determine the patient, physician, and institutional factors that affect the primary endpoint or secondary endpoints.

Primary Objective:

To determine whether length of hospital stay is significantly shortened in the interventional arm vs. SOC.

Hypothesis:

Adding cardiac CT to the initial ED evaluation of subjects with acute chest pain decreases length of hospital stay.

Part II: Study Description

1. Background and Significance

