3.2 Secondary Aims

1. To determine whether time to diagnosis is significantly shortened and rates of direct discharge from ED are increased in the interventional arm vs. SOC.

A) Time to Diagnosis:

For **ACS**: Defined as the time from ED presentation until the first test during index hospitalization that leads to the diagnosis of ACS (tests may be biomarkers, CTA, ETT, nuclear imaging, stress ECHO or cardiac catheterization), For no ACS: Defined as the time from ED presentation defined as the final test during index hospitalization.

B) Admission to Hospital: Participants are considered to be admitted if the ED attending admitted the subject to a hospital floor (medical floor, step down unit, telemetry hospital floor, or intensive care unit)

Direct ED Discharge will include all subjects who are not included in (B).

Hypothesis: *ED evaluation of subjects with acute chest pain supplemented by cardiac CT significantly increases direct ED discharge rates and shortens time to diagnosis for both ACS positive and negative patients.*

2. To determine a) the additional number of invasive coronary angiograms, both arms, and b) to determine the number of coronary revascularization procedures.

Hypothesis: *ED evaluation of subjects with acute chest pain supplemented by cardiac CT will not increase the number of invasive coronary angiograms without revascularization or revascularizations during index hospitalization.*

3. To determine the safety of immediate ED discharge after a normal cardiac CT defined as the occurrence of ACS within 48-72 hours after discharge.

Hypothesis: *CTA has a high negative predictive value based on which immediate ED discharge should not compromise patient safety.*

4. To determine whether subsequent testing and follow up, including invasive coronary angiograms, diagnostic (imaging) tests, interventions, repeat ED visits for cardiac related problems, and repeat hospitalizations for chest pain or equivalent during 28 days after hospital discharge is decreased in the interventional arm compared to SOC,.

Hypothesis: *Incorporation of CTA in the evaluation of acute chest pain patients in the ED will not lead to decreased further testing to manage chest pain when as compared to the SOC arm.*

5. To compare the two study arms in terms of rates of MACE (major adverse cardiac events—cardiac death, AMI, revascularization, unstable angina, and rehospitalization) within 28 days.

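### The overview gives the angiogram and revascularization endpoint as index stay and 28 days, but the non-inferiority tests stop at the end of the index visit, a time the intervention is meant to change; the comparison can be biased in either direction.

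*Protocol*

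**What the plan says.** The same endpoint appears with different windows in the Protocol.

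- **Part I, Study Overview.** Among the efficiency measures it lists invasive angiograms and "coronary revascularization procedures during index hospitalization and 28 days (secondary endpoint").
- **Study Synopsis, Secondary Hypothesis.** No window is given: "There will not be an increase in the number of invasive angiograms or coronary revascularization procedures as compared to the SOC arm".
- **Section 3.2, Aim 2.** The hypothesis is that CT "will not increase the number of invasive coronary angiograms without revascularization or revascularizations during index hospitalization".
- **Section 7.2.** The aim reads "To compare the two study arms in terms of cardiac health care utilization during the index visit". Of the angiogram count it says: "This secondary endpoint will be analyzed in terms of a non-inferiority trial". The margin is 5 points at one-sided 0.05, with 84% power from a 10% rate. Revascularization is treated the same way, with a 5% rate, a 3.5-point margin and 80% power.

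Two other places look at the period after discharge.

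- **Section 3.2, Aim 4** covers angiograms, imaging, interventions, repeat ED visits and "repeat hospitalizations for chest pain or equivalent during 28 days after hospital discharge is decreased in the interventional arm compared to SOC". Its section 7.2 counterpart is headed as utilization within one year, although section 5 now has no follow-up beyond 28 days.
- **Section 7.2** compares "rates of MACE (cardiac death, AMI, revascularization, unstable angina, and rehospitalization) within 28 days".

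**The concern.** A count that ends with the index visit ends at a time set after randomization. This trial is built to move that time in one arm: planned mean stay is 18.8 to 32.8 hours with CT against 40.5 hours, and planned direct ED discharge is 32% against 15%. The same procedure can count in one arm and not in the other only because of when the patient went home.

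The test concerned is important. Section 1.3 names extra angiograms (11 v 3 in an earlier randomized trial) as a potential drawback of CT. Section 7.2 chooses non-inferiority because a non-significant difference would not show that CT is no worse. A pass on the index visit alone does not establish that over the period named in the overview. Conversely, a failure could reflect only a shift in timing.

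**Working it through.** **Inputs.** n = 500 per arm (Synopsis). Angiograms: 10% per arm, margin 0.05, one-sided alpha 0.05 (section 7.2). Revascularization: 5% per arm, margin 0.035 (section 7.2). The document gives no share of procedures falling after discharge and no cumulative 28-day rate, so the shifts below are assumptions.

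**Formula.** With SE = √[pS(1−pS)/500 + pC(1−pC)/500], where S is standard care and C is CT, P(pass) = Φ[(margin − (pC − pS))/SE − 1.645].

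**The plan's own figures.**
- Angiograms, 10% v 10%: SE = √(2 × 0.10 × 0.90/500) = 0.01897; 0.05/0.01897 = 2.635; Φ(0.990) = 83.9%. Stated 84%: reproduced.
- Revascularization, 5% v 5%: SE = 0.01378; 0.035/0.01378 = 2.539; Φ(0.894) = 81.4%. Stated 80%: reproduced to within 2 points.

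**True cumulative angiogram rates at the margin (10% v 15%).** A valid test passes 5% of the time.

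| Assumed net shift to after discharge | Index rates, standard v CT | SE | P(pass) |
|---|---|---|---|
| none | 10% v 15% | 0.02086 | 5.0% |
| 1 point, CT arm | 10% v 14% | 0.02051 | Φ(0.488 − 1.645) = 12.4% |
| 2 points, CT arm | 10% v 13% | 0.02015 | Φ(0.992 − 1.645) = 25.7% |
| 1 point, standard arm | 9% v 15% | 0.02046 | Φ(−0.489 − 1.645) = 1.6% |
| 2 points, standard arm | 8% v 15% | 0.02005 | Φ(−0.997 − 1.645) = 0.4% |

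**No true difference (10% v 10%).** P(pass) is the power.

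| Assumed net shift to after discharge | Index rates, standard v CT | SE | P(pass) |
|---|---|---|---|
| none | 10% v 10% | 0.01897 | 83.9% |
| 1 point, standard arm | 9% v 10% | 0.01854 | Φ(2.157 − 1.645) = 69.6% |
| 2 points, standard arm | 8% v 10% | 0.01809 | Φ(1.659 − 1.645) = 50.5% |

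**Does the plan indicate a direction?** The planned CT-arm mean is a mixture: 0.486 × 6 + 0.288 × 10 + 0.226 × 57.9 = 18.9 hours, against 18.8 in the table. All the shortening is in participants with normal LV function and no CAD or only non-obstructive CAD. The remaining 22.6%, who include those with significant stenosis, keep a mean of 57.9 hours taken from ROMICAT I. The other indications conflict:
- Section 7.2 says some CT-arm patients may stay longer for procedures that the CT prompts.
- It expects more later cardiac work-up with standard care (29% v 14%), a figure for all work-up and not angiograms alone.
- Tertiary Aim 1 says CT may raise testing during follow-up.

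**Power over a longer window, no true difference.** The cumulative rate is unknown, so a range is shown.
- Angiograms, margin 0.05: 83.9% at a 10% rate, 81.1% at 11%, 78.5% at 12%.
- Revascularization, margin 0.035: 81.4% at 5%; at 6%, SE = √(2 × 0.06 × 0.94/500) = 0.01502 and Φ(2.330 − 1.645) = 75%.

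**The case against.** **The overview may be listing two periods.** Its sentence can be read as naming the index stay and 28 days separately, which Aims 2 and 4 then take up in turn. That is a fair reading and softens the contradiction. It does not supply a margin-based test over both periods, and the Synopsis claim of no increase still has no window.

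**Later procedures are not ignored.** A reader might infer that procedures after discharge go uncounted. They do not: Aim 4 covers angiograms and interventions in the 28 days after discharge, and 28-day MACE includes revascularization. Neither replaces the missing test, however. Aim 4 looks for a decrease and has no margin. MACE has no angiogram component, and Appendix B defines only urgent revascularization, so an elective procedure after a CT finding would not meet it.

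**The test leans towards a pass.** This is the tempting stronger reading, because the CT arm is meant to go home sooner. The document does not support it. The planned early discharges are in participants without obstructive disease, who are unlikely candidates for angiography. Patients with CT-indicated procedures may stay longer, and later work-up is expected to be commoner with standard care. One argument for a lean remains: if there is a true excess, equal proportional displacement shrinks the absolute difference. With 10% displaced in both arms, 10% v 15% becomes 9% v 13.5% and the false pass rate rises from 5% to about 8%. Equal displacement is itself an assumption, so the direction stays open.

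**Conclusion.** The point holds as an inconsistency of window and as a design weakness of the two non-inferiority tests. Their counting period ends at a time that depends on the arm, and no other stated analysis tests cumulative angiograms against a margin. The direction of any bias is undetermined.

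The effect could be material both ways. A net shift of 1 or 2 points takes the false pass rate at the margin from 5% to about 12% or 26% if it falls in the CT arm. It takes power at no difference from 84% to about 70% or 50% if it falls in standard care. These figures rest on assumed shifts and on the normal approximation, which reproduces the stated power. The power calculations themselves are not in dispute. The point concerns secondary endpoints and is worth correcting mainly because the correction is cheap.

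**What to change.** 1. In section 3.2 (Aim 2) and section 7.2, run both non-inferiority tests on procedures within one fixed period of equal length in both arms, for example 28 days from randomization with the index stay included. Choose one clock start: section 3.2 counts 28 days from index discharge, so index stay plus 28 days is not equal time in the two arms.
2. Keep the index-visit count as a supportive analysis.
3. Give the same window in the Synopsis hypothesis, the Study Overview, Aim 2 and section 7.2, and correct the obsolete one-year heading in section 7.2. In the same edit, settle whether the endpoint is all invasive angiograms (section 7.2) or those without revascularization (Aim 2 hypothesis).
4. Do not assert that the 10% and 5% rates apply to the new window, since section 7.2 gives no window for them. Restate angiogram power as a range: about 84% at a 10% rate, 81% at 11%, 78% at 12%. Treat revascularization likewise.

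**Cost.** Wording only. The 28-day call and record review in section 5.3 already collect the data, and the call falls at least 28 days after ED discharge, so it covers 28 days from randomization. Power is somewhat lower if the cumulative rate is higher. Participants not reached at 28 days will have missing procedure data, because the fallback in section 5.3 covers mortality only.
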